7.2.5.5. Subgroup analyses

A subgroup analysis of the proportion of participants achieving EXACT-defined recovery from the index exacerbation by Index Exacerbation Severity will be performed by including a treatment-by-severity term in the model.

7.2.5.6. Sensitivity and supportive analyses

Sensitivity analyses exploring the impact of any missing data, and changes to the definition of EXACT-defined recovery may be conducted and may be performed post-SAC.

7.2.6. COPD Assessment Test (CAT)

The COPD Assessment Test (CAT) is a patient completed questionnaire developed to measure the health status of patients with COPD. The CAT consists of eight items, each on a six-point scale: 0 (no impact) to 5 (high impact). The CAT Score will be calculated for each study day of collection by summing the scores for all questions. The CAT Score ranges from 0 to 40, where higher scores indicate a more severe condition.

7.2.6.1. Proportion of responders using the CAT

The proportion of responders using the CAT will only be derived for participants with a baseline CAT Total Score ≥ 2 .

The Proportion of responders using the CAT is defined as:

(Number of participants with a decrease from baseline in CAT Total Score ≥ 2 on or before Day X)/(Total number of participants in the MITT population)

Where Day X is 28, 56, and 84 and the study day following EXACT-defined recovery from the index exacerbation. See Section 13.2.1.2 for details for cases where the study day following EXACT-defined recovery occurs within a scheduled assessment window.

Note: due to software limitations of the electronic PRO device, the study day following EXACT-defined recovery is not derived according to the EXACT User Manual, see Section 13.2.1.2 for further details.

Exploratory – Follow-Up Period

The Proportion of responders using the CAT at Day 112 and 168 is defined as:

(Number of participants with a decrease from baseline in CAT Total Score ≥ 2 on or before Day X)/(Total number of participants in the MITT population)

Where Day X is Day 112 and Day 168 and the study day following EXACT defined recovery, if it occurs during the Follow-up period.

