2.1. Study Objective(s) and Endpoint(s)

Objectives	Endpoints
Primary Objectives	Primary Endpoints

 To characterise the dose response of nemiralisib administered in addition to SoC compared with placebo and SoC in participants diagnosed with an acute moderate or severe exacerbation of COPD 	
 Change from baseline in Clinic Visit trough forced expiratory volume in one second (FEV₁) at Day 84 measured post-bronchodilator
Secondary Objectives	Secondary Endpoints

 To characterise the dose response and efficacy of nemiralisib administered in addition to SoC compared with placebo and SoC in participants diagnosed with an acute moderate or severe exacerbation of COPD 	
 Rate of moderate and severe exacerbations over the 12-Week Treatment Period Time to next moderate/severe exacerbation following index exacerbation Change from baseline in Clinic Visit trough FEV₁ measured pre- and post-bronchodilator at Days 14, 28, 56, and 84 (Day 84: post-bronchodilator is the primary endpoint; pre-bronchodilator is a secondary endpoint) and at hospital discharge (only for participants who are hospitalized for the index exacerbation) Change from hospital discharge in clinic visit trough FEV₁ measured pre- and post-bronchodilator at Days, 14, 28, 56, and 84 (in participants hospitalized for index exacerbation only)

 To evaluate the treatment effect of nemiralisib in addition to SoC compared with placebo and SoC on symptoms indicative of an exacerbation and on health status using Patient-Reported Outcomes (PROs) in participants diagnosed with an acute moderate or severe exacerbation of COPD 	
EXAcerbations of Chronic Pulmonary Disease Tool (EXACT-PRO)
 
 Proportion of participants achieving the EXACT definition of recovery from the index exacerbation by Days 14, 28, 56, and 84 Time to recovery from index exacerbation Severity of subsequent HCRU-defined exacerbation(s) defined by EXACT 
COPD Assessment Test (CAT)
 
 Proportion of responders using the CAT at Treatment Days 28, 56, and 84, and following EXACT defined

Objectives	Endpoints

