
 To evaluate inflammatory markers in blood in relation to acute exacerbation of COPD 	
 Blood samples collected at Screening through Visit 7 (as part of the clinical laboratory blood samples) for analysis of blood eosinophil counts and inflammatory mediators Blood samples for analysis of inflammatory biomarkers (including but not limited to: high sensitivity C-reactive protein [hs-CRP], chemokine interferon-γ inducible protein 10 kDa (CXCL10)), and procalcitonin) collected at Visit 1 (Screening)

 To evaluate inflammatory and infective markers in sputum in relation to acute exacerbation of COPD 	
 Spontaneous sputum sample for analysis of inflammatory and infective markers collected at Screening/Day 1 (pre-dose) and Day 56 in participants who are willing and able to provide a sample

 To evaluate the potential post-treatment impact of double-blind study treatment during the 12-Week Post-Treatment Follow-Up Period 	
 Change from baseline (Day 84) in Clinic Visit trough FEV1 measured pre- and postbronchodilator at Day 112, 140 and 168 Rate of moderate and severe COPD exacerbation(s) during the 12-Week Follow-Up Period Rate of moderate and severe COPD exacerbation(s) over the 24 week study duration Time to next exacerbation following cessation of double blind study treatment Proportion of responders using the CAT at Days 112 and 168 Change from baseline (Day 1) in CAT Total score at Days 112 and 168 Proportion of responders on the SGRQ Total Score as measured by the SGRQ-C at Days 112 and 168 Change from baseline (Day 1) in SGRQ total score at

Objectives	Endpoints
	Days 112 and 168 
 • Severity of subsequent HCRU exacerbation defined by EXACT • E-RS: COPD and subscales from last dose of double-blind study treatment • Rescue medication use up to Day 112

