7.2.7.1. Proportion of responders on the SGRQ Total Score

The proportion of responders on the SGRQ Total Score will only be derived for participants with a baseline SGRQ Total Score ≥ 4 .

Proportion of responders on the SGRQ Total Score is defined as:

$$\frac{\text{(Number of participants with a decrease from baseline in SGRQ Total Score } \geq 4 \text{ on or before Day X)}}{\text{(Total number of participants in the MITT population)}}$$

Where Day X is 28, 56, and 84.

Exploratory – Follow-Up Period

The Proportion of responders on the SGRQ Total Score at Day 112 and 168 is defined as:

$$\frac{\text{(Number of participants with a decrease from baseline in SGRQ Total Score } \geq 4 \text{ on or before Day X)}}{\text{(Total number of participants in the MITT population)}}$$

Where Day X is Day 112 and Day 168 and the study day following EXACT defined recovery, if it occurs during the Follow-up period.

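### CAT and SGRQ responders are listed at each study day but derived cumulatively, so on-treatment response is carried into the Day 112 and Day 168 responder results

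*SAP*

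**What the plan says.** **Endpoint list (SAP 2.1).** The secondary CAT endpoint is "Proportion of responders using the CAT at Treatment Days 28, 56, and 84, and following EXACT defined" recovery. SGRQ responders are listed in the same way at Days 28, 56 and 84. Under the exploratory objective on post-treatment impact, the list has "Proportion of responders using the CAT at Days 112 and 168", with a matching SGRQ entry.

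**Derivation (SAP 7.2.6.1 and 7.2.7.1).** The CAT numerator is the "Number of participants with a decrease from baseline in CAT Total Score ≥ 2 on or before Day X", and the formula continues "on or before Day X)/(Total number of participants in the MITT population". It applies "Where Day X is 28, 56, and 84 and the study day following EXACT-defined recovery from the index exacerbation". The follow-up paragraph opens with "The Proportion of responders using the CAT at Day 112 and 168 is defined as" and then repeats the on-or-before formula with no new starting point. Section 7.2.7.1 uses the same structure with a threshold of 4, including "The Proportion of responders on the SGRQ Total Score at Day 112 and 168 is defined as". The earlier RAP versions in the same file carry the same rule.

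**Eligibility.** Section 7.2.6.1 also says that the CAT proportion "will only be derived for participants with a baseline CAT Total Score" of at least 2 (SGRQ: at least 4). The denominator is nevertheless the whole MITT population.

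**Use.** A separate Bayesian logistic model is fitted at each time-point (7.2.5.4, applied through 7.2.6.3 and 7.2.7.3). Appendix 11 lists the main displays by visit: Tables 2.29 and 2.32 at Interim Analysis 2, and Tables 2.71 and 2.81 at end of treatment and final reporting.

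**The concern.** Being a responder at a day and having responded by that day are different endpoints. The SAP keeps them apart elsewhere: EXACT recovery is listed in Section 2.1 as achieved by given days and is derived cumulatively in 7.2.5.1, which is consistent. For CAT and SGRQ the cumulative formula sits under an endpoint named for status at the day.

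The mismatch matters most in follow-up. The Day 112 and Day 168 endpoints serve the question of what happens after treatment stops. A participant who responded at Day 28 and then returned to baseline would still be counted as a responder at Day 168. A reader of a by-visit table would take that figure as current status.

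**Working it through.** The plan states no response rate or power for these endpoints, so there is no figure to reproduce. The check is one of logic, followed by an illustration.

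**Step 1: the rule applied to one participant.** Take CAT changes from baseline of -3, +1, +2, +2, +3 at Days 28, 56, 84, 112 and 168.

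- Scored at Day X: 1, 0, 0, 0, 0.
- Scored on or before Day X: 1, 1, 1, 1, 1.

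**Step 2: the general result.** Let r(v) be the responder indicator at visit v. The SAP indicator is R(X) = max of r(v) over v ≤ X, which never decreases in X. Divided by a fixed N (all MITT), the proportion cannot fall from Day 28 to Day 168. The CAT time-point after EXACT recovery differs between participants and lies outside this ordered series.

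**Step 3: illustrative size.** All rates and correlations here are assumptions. A participant responds at visit v if √ρ·b + √(1-ρ)·e_v exceeds t_v = Φ⁻¹(1-p_v), with b and e_v standard normal. The cumulative proportion is 1 - ∫ φ(b) ∏ Φ[(t_v - √ρ·b)/√(1-ρ)] db, the product running over visits up to X. With ρ = 0.6:

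| Day | At Day X, active v placebo | OR | On or before, active v placebo | OR |
|---|---|---|---|---|
| 28 | 60% v 50% | 1.50 | 60.00% v 50.00% | 1.50 |
| 56 | 60% v 50% | 1.50 | 74.26% v 64.76% | 1.57 |
| 84 | 60% v 50% | 1.50 | 80.74% v 72.14% | 1.62 |
| 112 | 45% v 45% | 1.00 | 82.44% v 75.65% | 1.51 |
| 168 | 45% v 45% | 1.00 | 83.79% v 78.21% | 1.44 |

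For Day 168: (0.8379/0.1621)/(0.7821/0.2179) = 5.169/3.589 = 1.44. Simulation of the same set-up gives 1.51, 1.58, 1.62, 1.51 and 1.44, which agrees to within 0.01.

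*Range.* For ρ from 0.8 to 0.4, the Day 84 odds ratio is 1.55 to 1.71 (at-visit 1.50) and the Day 168 odds ratio is 1.41 to 1.51 (at-visit 1.00). In a second scenario (active 60/60/60/50/45%, placebo 45% throughout, ρ = 0.7), Day 168 reads about 1.69 instead of 1.00.

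*Level.* With a constant 55% at every visit and ρ from 0.8 to 0.4, the cumulative proportion is 70% to 82% at Day 84 and 75% to 90% at Day 168.

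**Step 4: denominator.** If a share q of MITT is below the baseline threshold or has no baseline, a proportion p among eligible participants is reported as p(1-q). With p = 50%, assumed q of 2% gives 49% and q of 5% gives 47.5%.

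**Step 5: SGRQ follow-up time-point.** Section 7.2.7.1 adds the day after EXACT recovery to Days 112 and 168. No such SGRQ time-point appears in Section 2.1, in the treatment-period part of 7.2.7.1, or in 7.2.7.2. The clause matches the CAT wording.

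**The case against.** - **Loss of benefit is measured elsewhere.** A reader might infer that the trial cannot show loss of CAT or SGRQ benefit after treatment. The SAP does not support that. Sections 7.2.6.2 and 7.2.7.2 define change from baseline and change from Day 84 at Days 112 and 168 from the score on that day. Both are analysed by repeated measures, and the change-from-Day-84 displays are Tables 2.75 to 2.78 and 2.85 to 2.88. This objection stands: only the dichotomised version hides the loss.
- **The secondary comparison moves little.** At ρ = 0.6 the odds ratio is unchanged at Day 28 and 8% higher at Day 84 (1.62/1.50 = 1.08). This largely stands, although the shift reaches 14% at ρ = 0.4 (1.71/1.50 = 1.14), and the percentages themselves rise clearly.
- **No decision rule uses these endpoints.** The primary endpoint is FEV₁, futility uses FEV₁ and exacerbation rate (3.1.1.1), and adaptation uses the FEV₁ efficiency ratio (7.1.2). CAT and SGRQ responders are reviewed at Interim Analysis 2 but trigger nothing. This stands and limits the severity.
- **The denominator point is small, and the display is unclear.** Few patients enrolled during an exacerbation are likely to score below 2 on CAT or below 4 on SGRQ. Example Shell 9 shows an n beneath N. If percentages were taken over that n and it varied by visit, the proportion could fall. That is a further reason to settle text and shell, but the formula as written uses all MITT.
- **Renaming would remove the conflict.** Calling the endpoint a cumulative one would resolve the wording, but it would then no longer describe post-treatment status.

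**Conclusion.** The mismatch is real and follows from the text alone. Sections 7.2.6.1 and 7.2.7.1 derive a different quantity from the one Section 2.1 lists, and nothing else in the SAP restricts the count to the Day X score. It is material mainly for the exploratory Day 112 and Day 168 responder displays, where an effect fully lost off treatment could still appear as an odds ratio of about 1.4 to 1.7 under the assumed scenarios. The documents give neither response rates nor between-visit correlations, so these figures illustrate the mechanism and do not estimate it.

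Two stronger readings are not supported: that post-treatment loss of benefit goes unmeasured, and that the on-treatment responder comparison is seriously distorted. The eligibility and denominator conflict and the stray SGRQ time-point are genuine but minor. This should be fixed, but it does not threaten the trial's main conclusions.

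**What to change.** In Sections 7.2.6.1 and 7.2.7.1:

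1. Define the responder at Day X by the change from baseline in the score recorded at Day X.
2. Make the denominator match the eligibility rule: MITT participants with baseline CAT of at least 2, or baseline SGRQ of at least 4. Bring Example Shell 9 into line.
3. State how a missing Day X score is handled. Counting it as non-response is one acceptable choice; what matters is that a rule is written down.
4. Delete the EXACT-recovery time-point from the SGRQ follow-up definition.
5. If a cumulative count is wanted, keep it as a supportive display named as response by Day X.

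The cost is SAP wording and one derivation applied to both questionnaires. No new data are needed. Reported percentages after the first visit will generally be lower than under the cumulative rule.

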7.2.6.2. Change from baseline in CAT Total Score

Change from baseline in CAT Total Score is defined as:

$$\text{CAT Total Score on Day X} - \text{Baseline CAT Total Score}$$

Where Day X is 28, 56, 84 and the study day following EXACT defined recovery from the index exacerbation. See Section 13.2.1.2 for details for cases where the study day following EXACT-defined recovery occurs within a scheduled assessment window.

Note: due to software limitations of the electronic PRO device, the study day following EXACT-defined recovery is not derived according to the EXACT User Manual, see Section 13.2.1.2 for further details.

Exploratory – Follow-Up Period

The Change from baseline in CAT Total Score at Day 112 and 168 is defined as:

$$\text{CAT Total Score on Day X} - \text{Baseline CAT Total Score}$$

Where Day X is Day 112 and Day 168.

The Change from end of treatment in CAT Total Score at Day 112 and 168 is defined as:

$$\text{CAT Total Score on Day X} - \text{CAT Total Score on Day 84}$$

Where Day X is Day 112 and Day 168.

7.2.6.3. Statistical analyses

The proportion of responders using CAT will be analysed using the same techniques as described in Section 7.2.5.4.

Change from baseline/end of treatment in CAT Total Score will be compared between treatment groups using a Bayesian Repeated Measures analysis with covariates for baseline-by-Day interaction and treatment-by-Day interaction. Day will be fitted as a repeated effect within each participant.

All post-baseline scheduled visits will be included in the analysis using Day.

Non-informative priors will be used for all modelling parameters. Wherever possible conjugate priors will be utilised. An unstructured covariance matrix will be used to model the within-subject error.

Adjusted posterior median change from baseline and corresponding 95% HPD credible intervals will be summarised for each treatment by time-point, together with estimated treatment differences (GSK – Placebo) and corresponding 95% HPD credible intervals. The posterior probability that the true treatment difference is less than 0, in addition to other values appropriately selected based on the data, will also be presented.

7.2.6.4. Subgroup analyses

A subgroup analysis of the proportion of responders using CAT and the change from baseline in CAT Total Score by Index exacerbation severity will be performed by including a treatment-by-severity term and a treatment-by-severity-by-Day term in the Bayesian logistic regression and Bayesian Repeated Measures models, respectively.

7.2.7. St. George's Respiratory Questionnaire for COPD Patients (SGRQ-C)

St. George's Respiratory Questionnaire for COPD Patients (SGRQ-C) is a 40-item questionnaire designed specifically to focus on COPD patients. SGRQ-C will be scored to be equivalent to the SGRQ Total Score, ranging from 0 to 100, where higher scores reflect worse health-related quality of life. SGRQ Total Scores will be calculated for each day of collection according to the instructions in SGRQ-C Manual (Version 1.3, March 2016).

7.2.7.1. Proportion of responders on the SGRQ Total Score

The proportion of responders on the SGRQ Total Score will only be derived for participants with a baseline SGRQ Total Score ≥ 4 .

Proportion of responders on the SGRQ Total Score is defined as:

$$\frac{\text{(Number of participants with a decrease from baseline in SGRQ Total Score } \geq 4 \text{ on or before Day X)}}{\text{(Total number of participants in the MITT population)}}$$

Where Day X is 28, 56, and 84.

Exploratory – Follow-Up Period

The Proportion of responders on the SGRQ Total Score at Day 112 and 168 is defined as:

$$\frac{\text{(Number of participants with a decrease from baseline in SGRQ Total Score } \geq 4 \text{ on or before Day X)}}{\text{(Total number of participants in the MITT population)}}$$

Where Day X is Day 112 and Day 168 and the study day following EXACT defined recovery, if it occurs during the Follow-up period.

7.2.7.2. Change from baseline in SGRQ Total Score

Change from baseline in SGRQ Total Score is defined as:

$$\text{SGRQ Total Score on Day X} - \text{Baseline SGRQ Total Score}$$

Where Day X is Day 28, 56, and 84.

Exploratory – Follow-Up Period

The Change from baseline in SGRQ Total Score at Day 112 and 168 is defined as:

SGRQ Total Score on Day X – Baseline SGRQ Total Score

Where Day X is Day 112 and Day 168.

The Change from end of treatment in SGRQ Total Score at Day 112 and 168 is defined as:

SGRQ Total Score on Day X – SGRQ Total Score on Day 84

Where Day X is Day 112 and Day 168.

7.2.7.3. Statistical analyses

Change from baseline/end of treatment in SGRQ Total Score and the proportion of responders on the SGRQ Total Score will be analysed using the same techniques as described in Section [7.2.6.3](#).

7.2.7.4. Subgroup analyses

Subgroup analyses of change from baseline in SGRQ Total Score and the proportion of responders on the SGRQ Total Score by Index exacerbation severity will be conducted as described in Section [7.2.6.4](#).

7.2.8. Rescue medication use

All participants will record rescue medication use in the eDiary. Rescue medication use will be recorded as the number of occasions of rescue medication use each day.

The Mean Number of Occasions of Rescue Medication Use Per Day is defined as:

$$\frac{\text{(Sum of the number of occasions of rescue medication use each day within the time-period)}}{\text{(Total number of days with non-missing values within the time-period)}}$$

The Percentage of Rescue-Free Days is defined as:

$$\frac{\text{(Sum of the number of days where the number of occasions of rescue medication use is zero within the time-period)}}{\text{(Total number of days with non-missing values within the time-period)}} * 100$$

Where the time-period is defined as follows:

Week 1 of the 12-Week Treatment Period: Day 1 to Day 7

Week 2 of the 12-Week Treatment Period: Day 8 to Day 14

Week 3 of the 12-Week Treatment Period: Day 15 to Day 21

Week 4 of the 12-Week Treatment Period: Day 22 to Day 28

Week 5 of the 12-Week Treatment Period: Day 29 to Day 35

Week 6 of the 12-Week Treatment Period: Day 36 to Day 42

Week 7 of the 12-Week Treatment Period: Day 43 to Day 49

Week 8 of the 12-Week Treatment Period: Day 50 to Day 56

Week 9 of the 12-Week Treatment Period: Day 57 to Day 63

Week 10 of the 12-Week Treatment Period: Day 64 to Day 70

Week 11 of the 12-Week Treatment Period: Day 71 to Day 77

Week 12 of the 12-Week Treatment Period: Day 78 to Day of last dose

Over the 12-Week Treatment Period: Day 1 to Day of last dose.

Exploratory – Follow-Up Period

Rescue medication use up to Day 112 will also be summarised by including the time-periods:

Week 13 (Follow-up Period): (Day of last dose + 1) to (Day of last dose + 1) + 6 days

Week 14 (Follow-up Period): (Day of last dose + 7) to (Day of last dose + 1) + 13 days

Week 15 (Follow-up Period): (Day of last dose + 14) to (Day of last dose + 1) + 20 days

Week 16 (Follow-up Period): (Day of last dose + 21) to (Day of last dose + 1) + 27 days

For a subject to be counted in the time periods for rescue medication use, they must have at least one eDiary entry recorded during that time period.

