7.2.8.2. Statistical analyses

The Mean Number of (on-treatment) Occasions of Rescue Medication Use Per Day will be summarised between each treatment group using means, standard deviations, medians, minimum and maximum.

The Percentage of (on-treatment) Rescue-Free Days will be summarised between each treatment group using means, standard deviations, medians, minimum and maximum.

Rescue medication use via the clip-on Propeller Sensor for MDI will be summarised in the same way as rescue medication use via the eDiary.

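### Rescue-medication follow-up Weeks 14 to 16 each start one day early and overlap the preceding week, and the plan does not say whether treatment Weeks 1 to 11 are cut at last dose

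*SAP*

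**What the plan says.** Section 7.2.8 defines two per-day measures, mean occasions of rescue use and percentage of rescue-free days. Each is divided by the number of days in the window that have a diary value, and one diary entry is enough for a participant to count in a window.

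- **Treatment weeks.** Weeks 1 to 11 are fixed 7-day blocks of study days, for example "Week 5 of the 12-Week Treatment Period: Day 29 to Day 35". Week 12 is different: "Week 12 of the 12-Week Treatment Period: Day 78 to Day of last dose". The overall treatment-period summary also stops at the day of last dose.
- **Follow-up weeks (exploratory).** The stated aim is "Rescue medication use up to Day 112 will also be summarised by including the time-periods". The first of the four windows is "Week 13 (Follow-up Period): (Day of last dose + 1) to (Day of last dose + 1) + 6 days". The second, which already shows the fault, is "Week 14 (Follow-up Period): (Day of last dose + 7) to (Day of last dose + 1) + 13 days". The third repeats the pattern with "Week 15 (Follow-up Period): (Day of last dose + 14) to (Day of last dose + 1) + 20 days". The fourth and last is "Week 16 (Follow-up Period): (Day of last dose + 21) to (Day of last dose + 1) + 27 days".
- **Analysis.** Section 7.2.8.2 states: "The Mean Number of (on-treatment) Occasions of Rescue Medication Use Per Day will be summarised". Rescue-free days carry the same on-treatment qualifier.
- **Sensor data.** Section 7.2.8.1 defines sensor-recorded use in the same way, so it inherits the windows.

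All three versions of the plan in the file carry these windows.

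**The concern.** Two things look wrong.

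First, the follow-up windows are labelled as consecutive weeks, but each of Weeks 14 to 16 appears to begin on a day that already belongs to the week before. A programmer following the text would produce overlapping weeks of unequal length.

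Second, the treatment weeks follow two rules. Week 12 and the overall period are cut at last dose; Weeks 1 to 11 are not, although section 7.2.8.2 calls the summaries on-treatment. The plan expects some participants to stop treatment early and stay in the study: sections 7.2.1 and 13.3.2 separate on-treatment from on- or off-treatment exacerbations, and section 7.3.1 excludes early stoppers from one analysis. For such a participant the fixed treatment weeks run on past last dose, while the follow-up weeks start the day after it, so the same diary days can fall under both headings.

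Weekly rescue use and rescue-free days are secondary endpoints in section 2.1. They are tabulated at Interim Analysis 2, at the End of Treatment analysis and in the final report, so two programmers should not be able to derive different values from the same text.

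**Working it through.** **Inputs.** The window definitions are those of section 7.2.8. LD is the day of last dose.

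**Reproducing the plan's own figure.** With LD = 84, Week 16 ends on (84 + 1) + 27 = Day 112, as the plan intends. The end days are right, so the fault lies in the start days.

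**Expanding the follow-up windows.**

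| Week | Start | End | Days | With LD = 84 |
|---|---|---|---|---|
| 13 | LD+1 | (LD+1)+6 = LD+7 | 7 | 85–91 |
| 14 | LD+7 | (LD+1)+13 = LD+14 | 8 | 91–98 |
| 15 | LD+14 | (LD+1)+20 = LD+21 | 8 | 98–105 |
| 16 | LD+21 | (LD+1)+27 = LD+28 | 8 | 105–112 |

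The lengths sum to 7 + 8 + 8 + 8 = 31 day-slots, but LD+1 to LD+28 holds 28 distinct days. The three extra slots are LD+7, LD+14 and LD+21 (Days 91, 98 and 105 when LD = 84). This holds for any LD.

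Section 13.5.1 supports reading it as a slip. It counts post-treatment time so that LD+1 is day 1, which makes LD+8 the first day of the second week.

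**Effect on a weekly value.** With a complete diary, adding a day with value x to seven days with mean m gives (7m + x)/8, a shift of (x − m)/8. For rescue-free days, x is 0 or 100, so the shift is at most 100/8 = 12.5 percentage points for one participant in one week. It can be larger when few diary days are present, and a participant whose only entry in the Week 14 window is on LD+7 enters Week 14 on that day alone.

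**Corrected starts.** With LD+8, LD+15 and LD+22 and LD = 84, the windows are Days 85–91, 92–98, 99–105 and 106–112: 7 days each, 28 in all, no overlap, ending on Day 112.

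**Treatment weeks, read literally.** Week 11 ends on Day 77, and Week 12 is cut at LD. Off-treatment days inside Weeks 1 to 11 therefore number 77 − LD when LD is below 77, and none otherwise. The follow-up weeks cover 28 distinct days after LD, so the number of these days used again is the smaller of 28 and 77 − LD.

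| LD | Off-treatment days in Weeks 1–11 | Used again in Weeks 13–16 |
|---|---|---|
| 77 or later | 0 | 0 |
| 60 | 77 − 60 = 17 (Days 61–77) | 17 |
| 30 | 77 − 30 = 47 (Days 31–77) | 28 (Days 31–58) |
| 10 | 77 − 10 = 67 (Days 11–77) | 28 (Days 11–38) |

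With LD = 30, Week 5 is mixed and Weeks 6 to 11 lie wholly after last dose. These are maximum counts; they need a diary entry on each of those days.

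**The case against.** **The overlap does little harm.** It sits only in the exploratory follow-up weeks. Both measures are per-day averages, so an 8-day window does not inflate them. The plan defines no total across Weeks 13 to 16, so no single statistic counts a day twice; the day appears in two adjacent rows. The summaries are descriptive, and rescue use plays no part in the futility rules. All of this stands. It limits the consequence but does not make the windows right.

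**The on-treatment qualifier may itself be the cut.** Section 2.1 speaks of weeks of treatment, and a week after last dose is arguably not one. Section 13.3.2 ends the on-treatment phase at treatment stop for exacerbations. On that reading no off-treatment day enters Weeks 1 to 11, and none is reused. The reading is tenable. Against it, section 7.2.8 writes the cut for Week 12 and for the overall period, which would be unnecessary if the qualifier did the work everywhere, and section 13.3.1.1 assigns the 12-week treatment period to Days 1 to 84 without reference to stopping. The text leaves the rule open.

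**A stronger reading to avoid.** A reader might infer that off-treatment days certainly contaminate the weekly secondary endpoints and distort comparisons between arms in the later weeks, perhaps by assuming some share of early stoppers such as 15%. The document does not support that. It gives no discontinuation rate, overall or by arm, and no figure for diary completion after stopping, and the qualifier can be read as a filter.

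**Conclusion.** The overlap is a definite arithmetic error for any day of last dose: three days fall in two weekly rows, and Weeks 14 to 16 have 8 days instead of 7. It affects exploratory descriptive rows only.

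The treatment-week point is an unresolved rule. Weeks 1 to 11 carry no written cut at last dose, whereas Week 12 and the overall period do, under summaries called on-treatment. Off-treatment days enter Weeks 1 to 11 only on the literal reading, only for a last dose before Day 77, and only if the diary is still completed after stopping. At most 28 days per participant are then used under both headings.

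The overall 12-week rescue result and the primary endpoint are unaffected. The size and direction of any effect on differences between arms cannot be stated from the document.

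**What to change.** 1. In section 7.2.8, start Weeks 14, 15 and 16 at LD+8, LD+15 and LD+22, and leave the end days as they are.
2. For the on-treatment weekly summaries, state that each of Weeks 1 to 11 ends at the earlier of its last study day and LD, as Week 12 and the overall period already do. Alternatively, drop the on-treatment qualifier from the weekly summaries in section 7.2.8.2 and say that they cover study days whether or not treatment continues.
3. Confirm that the same windows apply to the sensor summaries in section 7.2.8.1.

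The cost is three numbers and one clause in the plan, and a small change to the derivation program. No new data are needed.
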